8. ASSESSMENTS

8.1. Medical History

Medical history should list all ongoing conditions, significant historical conditions, surgical sterilizations, postmenopausal onset and onset of T1DM. Any changes in the patient's medical

condition from screening until the time of dosing during the placebo run-in period should be captured as medical history except for SAEs and events associated with study specific procedures which will be captured as AEs as noted in Section 9.2.

8.2. Body Measurements

Height (cm or in) will be measured at the Screening Visit, without shoes.

A single body weight recording will be made at each of the pre-defined nominal time points outlined in the [SCHEDULE OF ACTIVITIES \(Sentinels\)](#) and Screening, Week -2, Week 0/Day 1, Week 2, Week 4, Week 6, Week 8, Week 12, Early Termination (if applicable) and Follow-Up for Part 1. In Part 2, a single body weight recording will be made at Screening, Week -2, Week 0/Day 1, Week 2, Week 6 and Week 12, Early Termination (if applicable) and Follow-Up.

Weight will be recorded using a calibrated scale (with the same scale used for the duration of the study) which reports weight in either pounds or kilograms.

Weight measurements must be undertaken under standardized conditions, including patients wearing undergarments and a hospital gown (and no shoes) or minimal clothing with no shoes or heavy accessories (e.g., jewelry or belt).

BMI will be calculated as body weight (kg)/height (m)².

8.3. Physical Examination

A complete physical examination will be conducted by a physician, trained physician's assistant, or nurse practitioner at Screening. The complete examination will include the following: head, eyes, ears, nose, mouth, throat, abdomen, and skin; respiratory system, cardiovascular system, musculoskeletal system; central and peripheral nervous system, and lymphatic system.

A limited physical exam will be conducted at Day 1 and Day 21 (Sentinels) and Week 0/Day 1, Week 6 (Part 1 only) and Week 12 (Part 1 and Part 2) [and Early Termination, if applicable] and will include brief exam of: HEENT (head, eyes, ears, nose, throat), skin, heart, lungs, abdomen, and extremities.

Clinically significant physical examination changes that occur after dosing during the placebo run-in period will be captured as an adverse event.

8.4. 12-Lead ECG

Supine 12 lead ECGs will be obtained at the predefined nominal timepoints outlined in the [SCHEDULE OF ACTIVITIES \(Sentinels\)](#) and Screening, Week -2, Week 0/Day 1, Week 2, Week 4, Week 6, Week 8, Week 12, Early Termination (if applicable) and Follow-Up for Part 1. In Part 2, ECG recordings will be made at Screening, Week -2, Week 0/Day 1, Week

2, Week 6 and Week 12, Early Termination (if applicable) and Follow-Up. ECGs should be performed in triplicate at Week 0/Day 1 (Part 1 and 2) and as single values at all other visits. ECGs should be obtained prior to blood collection and prior to dosing.

- 12 lead ECGs should be performed after the patient has rested quietly for at least 10 minutes in a supine position.
- ECGs should be performed in triplicate at Day 1 (Sentinels) or Week 0/Day 1 (Part 1 and 2) and as single tracings at all other visits.
- Each original recording will be evaluated by the PI or designee following the measurement. The interpretation of results will follow the categories “normal,” “abnormal, NCS,” or “abnormal, CS.” Abnormal interpretations must include the specific nature of the abnormality (ies), (e.g. left bundle branch block, bradycardia, old MI). An abnormal measurement may be repeated at the discretion of the PI or designee. If an abnormal ECG measurement made after dosing is considered clinically significant, the abnormality will be recorded as an AE in the EDC.

8.5. Vital Signs

Vitals should be collected at the predefined nominal timepoints outlined in the SCHEDULE OF ACTIVITIES for Sentinels and sitting vital signs (blood pressure and pulse rate) will be measured at Screening, Week -2, Week 0/Day 1, Week 2, Week 4, Week 6, Week 8, Week 12, Early Termination (if applicable) and Follow-Up for Part 1. In Part 2, vital signs will be measured at Screening, Week -2, Week 0/Day 1, Week 2, Week 6 and Week 12, Early Termination (if applicable) and Follow-Up.

Vitals should be performed in triplicate at Week 0/Day 1 (Part 1 and 2) and as single values at all other visits.

Vitals should be collected via an automated device using an oscillometric (and not auscultatory) method as follows:

- Sitting blood pressure and pulse rate will be measured with the patient’s arm supported at the level of the heart and recorded to the nearest mmHg. The same arm will be used throughout the study. The patient should be rested and sitting with both feet on the ground for at least 5 minutes before the blood pressure is obtained.
- Assessment of pulse rate may be manual or from an automated device. However, when done manually, pulse rate must be measured in the brachial/radial artery for at least 30 seconds. The method for measuring pulse rate should be used consistently for each patient throughout the study.
- Assessment of vitals should be undertaken before collection of blood samples.
- Vitals should be performed in triplicate at Week 0 (Part 1 and 2) and as single values at all other visits.

- In the Sentinel phase, after conducting the sitting blood pressure, **patients will stand and standing blood pressure** (orthostatic blood pressure) will be measured within 2 minutes. Standing blood pressure will be performed as single value.

Out of range vital signs as defined in Appendix 3 (Values or Changes Potentially of Clinical Concern) will be reviewed by the PI or designee and designated as CS or NCS. Vitals may be repeated at the PI or designee discretion. If the abnormal vital signs are observed after dosing and considered clinically significant, the abnormality will be recorded as an AE in the EDC.

8.6. MMTT (SENTINELS ONLY)

Patients will be instructed to target a fasting blood glucose between 80 and 200 mg/dL for visits where MMTT will be conducted (Sentinels: Days -7, 1, 8, 15 and 21).. MMTT will be conducted at least 4 hours after the last bolus of insulin (except for the insulin bolus within 15 minutes of the MMTT) and at least 1 hour after any glucose tablet consumption. MMTTs not following these rules will be excluded from analysis of post meal response.

- If the patient's blood glucose is >200 mg/dL upon arrival to the clinic, the patient will be given TTP399 and pharmacokinetic samples will be taken according to the Schedule of Activities and MMTT conducted accordingly (starting 1 hour after dosing). If after 45 minutes of dosing with TTP399, blood glucose is still > 200 mg/dL, a correction dose of insulin along will be given prior to the MMTT. The MMTT will be initiated 60 minutes after the dose of TTP399 was administered. If a correction dose of insulin is administered, the pharmacodynamic blood samples will NOT be taken.
- If the patient's blood glucose is below 70 mg/dL, the patients will be treated with glucose. Once glucose levels are above 80 mg/dL, the patient will be given TTP399 and pharmacokinetic samples will be taken. An hour after dosing, the MMTT will be conducted according to the SCHEDULE OF ACTIVITIES and pharmacodynamic samples will be collected (Figure 5, Sentinels).

Patients will be dosed with 50% of their normal bolus mealtime insulin within 15 minutes of the MTTT. If patients change their normal bolus mealtime insulin during the study, the normal bolus mealtime insulin will be considered the current insulin dose.

To initiate the MMTT, patients will receive 1 bottle of Ensure Plus Homemade Vanilla Liquid [350 calories, 8 fl oz (237ml), 51 g carbohydrate, 11 g fat, 13 g of protein] in place of their morning meal. Patients will be required to consume the Ensure Plus within 5 minutes and the time of the first sip should be recorded as the start time in the EDC.

All MMTTs will be conducted under close medical supervision so insulin dose adjustments can be made quickly if necessary. If the patient meets the rescue criteria of having a glucose readings > 450mg/dL and is symptomatic (e.g. vomiting) or is unwilling to continue, the patient should be dosed with insulin to correct high glucose levels under normal standards of

care at the Investigator's (or Designee) discretion. The event should be recorded as hyperglycemia associated with MMTT in the patient's CRF.

8.6.1. Basal and Bolus Insulin Adjustments (Sentinel phase only):

The patient, in collaboration with site team, will adjust bolus insulin to aim for glucose levels consistent with ADA goals of a postprandial glucose of less than 180 mg/dL and before meal glucose levels 80-130 mg/dL. If the first dose of TTP399 does not significantly curtail glucose post-prandially, patients will be given either 25%, 50% or 75% of normal carbohydrate associated insulin dose for their next meal (based on the magnitude of the glucose spike in comparison to their baseline MMTT) and 100% of correction associated peak. Higher doses up to 100% of normal carbohydrate dosing will be administered based on glycemic responses after subsequent meals.

Basal rates will be adjusted to keep glucose levels flat or slightly increasing between meals (according to ADA goals of 80-130 mg/dL pre-prandially). Basal rates will be **specifically** evaluated on Days 3 and 6, based on blood glucose levels on 2 of the last 3 days

8.6.2. Standardized lunch following MMTT (Sentinel Phase only):

For all clinic visits when MMTTs are conducted, the patients will be given lunch with a standardized carbohydrate content (between 30-100 g of carbohydrate). Each patient will select a lunch on Day -7 (Sentinel). The same lunch will be provided at all visits requiring MMTTs. The amount of carbohydrates in the meal will be recorded in the EDC.

8.6.3. Dinner requirements following MMTT (Sentinel Phase only):

For all-day study visits with MMTTs and PK collection, an evening meal with a standardized carbohydrate content (between 30-100 g of carbohydrate) will be provided by the site. For the baseline MMTT where no PK is collected (i.e. a shorter clinic visit), patients are not required to stay in the clinic until dinner, but should have a dinner meal with between 30-100 g of carbohydrates and record the carbohydrate content in their CGM (Sentinels).

8.6.4. Sampling Schedule for MMTT (Pharmacokinetic and Pharmacodynamic Samples) (Sentinel Phase only)

Pharmacodynamic Samples

Sentinels

- Glucose samples will be obtained prior to MMTT time 0 (MMTT) and 30, 60, 90, 120, 150, and 180 min following the MMTT with every MMTT.
- C-peptide samples will be obtained prior to MMTT (time 0, MMTT and at 60min post MMTT (60, MMTT) at baseline (Day -7) and at last dose (Day 21) if patient has detectable c-peptide at Day -7.

- A Glucagon/GLP-1 sample will be obtained prior to MMTT (time 0, MMTT and at 10, 20, 30, 60 and 120 min post MMTT (60, MMTT) at baseline (Day -7) and at last dose (Day 21)

Pharmacokinetic Samples (Sentinel Phase only)

Sentinels

[figure not shown]
- On Day 1, Day 8, Day 15 and Day 21, blood samples will be obtained for TTP399 concentrations immediately prior to dosing at time 0 (PK) and 60, 90, 120, 150, 180, 240, 360 (6hr) and 540min (9hr) relative to dosing. On Day 22 (or the day AFTER the last dose administered in the clinic) an additional 24hr PK sample will be obtained (a window of 3 hours is allowable for the 24hr PK sample).

Retention Samples (Sentinel Phase only)

Sentinels

- Retention samples will be collected for non-genomic biomarkers (as applicable based on consent) at time 0, MMTT and at 60min post MMTT (60, MMTT) at baseline (Day -7) and at last dose (Day 21)

Figure 5: Sampling schedule for MMTT in Sentinel Phase

* In the Sentinel phase, a 24 hr PK sample will be taken approximately 24 hours (with a 3 hour window) after the last dose administered in the clinic (Day 22 or ET)

** c-peptide and glucagon/GLP-1 will be collected ONLY on Day -7 and Day 21 (or ET, if applicable)

*** The retention samples will only be collected for patients who consent

8.7. Safety and Efficacy Laboratory Assessments**8.7.1. Blood Volume**

Total blood sampling volume from each individual patient for scheduled visits is estimated to be approximately 360 mL for Sentinel patients, 148 mL for Part 1 patients and 123mL for Part 2 patients, as shown below.

C O N F I D E N T I A L

Investigational Product: TTP399
 Protocol Number: TTP399-203

Amendment5/FINAL
 Date: 08FEB2019

Table 1 Summary of Frequency and Approximate Volume of Blood Collection

Summary of Frequency and Approximate Volume of Blood Collection - Sentinels

SENTINELS Sample Type	Maximum proposed sample Volume (mL)	Number of Sampling Times				Total Volume ^a (mL)
		Screening /Baseline MMTT	Dose escalation Period	Follow-Up Visit (F/U)	Total Number of Samples	
Clinical Laboratory Tests (hematology and chemistry)	10.5	1	4	1	6	63
HbA1c	4	1	2		3	12
Plasma glucose with MMTT	2	1X7	4X7		35	70
c-peptide with MMTT	2	1X2	1X2		4	8
Glucagon and GLP-1 w MMTT ^b	2	1X6	1X6		12	24
PK (TTP399)	4	---	4X11	---	44	160
Retention sample (optional)	4	1X2	1X2		4	16
TOTAL						353

a. Additional blood samples/volume may be taken for repeats and safety testing.
b. In addition to glucagon and GLP-1 additional exploratory analytes that may be analyzed in the glucagon/GLP-1 sample include amylin, ghrelin, GIP, IL-6, Leptin, MCP-1, PP, PYY and TNF- α

C O N F I D E N T I A L

Investigational Product: TTP399
Protocol Number: TTP399-203Amendment5/FINAL
Date: 08FEB2019**Table 1 – Summary of Frequency and Approximate Volume of Blood Collection- Part 1**

PART 1 Sample Type	Maximum proposed sample Volume (mL)	Number of Sampling Times				Total Volume ^a (mL)
		Screening	Double- Blind Treatment	Follow-Up Visit (F/U)	Total Number of Samples	
Clinical Laboratory Tests (hematology, chemistry, and glycemic markers ^b)	10.5	1	6	1	8	84
HbA1c	4	1	6		7	28
Fasting c-peptide	2		2		2	4
Fasting glucagon and GLP- 1 ^c	2		2		2	4
PK (TTP399)	4	---	6	---	6	24
Retention sample (optional)	4		2	---	2	4
TOTAL						148

a. Additional blood samples/volume may be taken for repeats and safety testing.
b. In addition to HbA1c, glycemia biomarkers to be collected in Part 1 include fructosamine and Glycomark (1,5 anhydroglucitol)
c. In addition to glucagon and GLP-1 additional exploratory analytes (non-genomic) that may be analyzed in the glucagon/GLP-1 sample include amylin, ghrelin, GIP, IL-6, Leptin, MCP-1, PP, PYY and TNF- α

Table 1 - Summary of Frequency and Approximate Volume of Blood Collection- Part 2

PART 2 Sample Type	Maximum proposed sample Volume (mL)	Number of Sampling Times				Total Volume ^a (mL)
		Screening	Double- Blind Treatment	Follow-Up Visit (F/U)	Total Number of Samples	
Clinical Laboratory Tests (hematology, chemistry and glycemia biomarkers ^b)	10.5	1	4	1	6	63
HbA1c	4	1	4	1	6	24
PK (TTP399)	4	---	3	---	3	12
Fasting c-peptide	2	-	3	-	3	6
Fasting Glucagon ^c	2		3		3	6
Retention sample (optional)	4	---	3	---	3	12
TOTAL						123

a. Additional blood samples/volume may be taken for repeats and safety testing.
b. In addition to HbA1c and glucagon, glycemic biomarkers to be collected in Part 2 include fructosamine, 1,5 anhydroglucitol, and c-peptide
c. In addition to glucagon additional exploratory analytes (non-genomic) that may be analyzed in the glucagon sample include amylin, ghrelin, GLP-1, GIP, IL-6, Leptin, MCP-1, PP, PYY and TNF- α

8.7.2. Clinical Laboratory Assessments

The clinical laboratory tests listed in Table 2 will be performed at the pre-specified timepoints outlined in the [SCHEDULE OF ACTIVITIES](#) and Appendix 2 for Part 1 indicated for the specific part of the study. At all visits after giving informed consent, patient will report to the site prior to their morning meal. Unscheduled clinical lab tests may be obtained at any time during the study to assess any perceived safety concerns.

Efforts should be made to obtain all blood samples at a similar clock time (e.g., 0800 hours) at each visit to the study site.

Results that are out of range will be interpreted as “abnormal, not clinically significant (NCS),” or “abnormal, clinically significant (CS).” An abnormal laboratory result may be repeated at the PI’s or licensed physician designee’s discretion. If the abnormal laboratory result is considered clinically significant and occurs after dosing, the abnormality will be recorded as AE in the EDC.

Refer to Section 9.1 for the criteria for determining whether an abnormal laboratory test

finding should be reported as an adverse event.

All biological samples will be assayed by a Sponsor-identified laboratory using a validated analytical method. Details regarding the sample processing, handling, storage, and shipment will be described in the study-specific central laboratory manual prior to the initiation of the study.

Table 2 Laboratory Tests

Hematology	Chemistry	Glycemic markers	Urinalysis	Others
Hemoglobin	BUN	HbA1c	Specific Gravity	Pregnancy test (urine)
Hematocrit	Creatinine	Fructosamine (Part 1 and 2 only)	pH	Urine drug screen ^c
RBC Count	Ca ⁺⁺ (total)	1,5 anhydroglucitol (Part 1 and 2 only)	Glucose (qual)	
MCH, MCV, MCHC & RDW	Electrolytes (Na:K, Cl)	Fasting Ultra sensitive C-peptide (Part 1 and 2 only)	Protein (qual)	
Platelet Count	Total CO ₂ (Bicarbonate)		Blood (qual)	Lipid panel (total cholesterol, HDL-C, LDL-C, triglycerides)
WBC Count	AST/ ALT		Ketones	
Leukocyte differential (percent and total neutrophils, monocytes, eosinophils, basophils, lymphocytes)	Alkaline Phosphatase	Fasting Glucagon (Part 1 and 2 only)	Leukocyte esterase	PD Markers with MMTT (Sentinels only) ^d
	Total bilirubin		Nitrites	Ultra sensitive C-peptide
	Direct (conjugated) bilirubin ^a		Microscopy ^b	Glucose, Glucagon, GLP-1
	Uric Acid			
	Albumin			
	Total Protein			
	Ketones			
	Lactate			
	Free fatty acids			
	GGT (Part 1 and 2)			
	Fasting plasma glucose			

RBC: red blood cell; WBC: white blood cell; MCH: Mean Corpuscular Hemoglobin; MCV: Mean Corpuscular Volume; MCHC: Mean Corpuscular Hemoglobin Concentration; RDW: RBC Distribution Width; Abs: absolute; BUN: blood urea nitrogen; Ca⁺⁺: calcium; Na⁺: sodium; K⁺: potassium; Cl⁻: chloride; AST (SGOT): aspartate aminotransferase (serum glutamic oxaloacetic transaminase); ALT (SGPT): alanine aminotransferase (Serum glutamic pyruvic transaminase); qual: qualitative; HDL-C: high density lipoprotein cholesterol; LDL-C: low density lipoprotein cholesterol

a. Direct bilirubin will be measured at Screening. During the Treatment Period, both direct and indirect bilirubin will ONLY be measured when total bilirubin is greater than upper limit of the reference range.

If total bilirubin is lower than the upper limit of the reference range, neither direct nor indirect bilirubin will be measured

- b. Only if dipstick is positive for blood, protein, ketones, leukocyte esterase, or nitrites. Microscopy will include epithelial cells, red blood cells, white blood cells, bacteria, casts (hyaline, granular, cellular), crystals, and mucus.
- c. At Screening and Baseline for Part 2 only, and at additional times if needed based on PI discretion.
- d. In addition to glucagon and GLP-1 additional exploratory analytes (non-genomic) that may be analyzed in the glucagon/GLP-1 sample include amylin, ghrelin, GIP, IL-6, Leptin, MCP-1, PP, PYY and TNF- α

Pregnancy test (urine) should be obtained from women of childbearing potential at each visit and for women of non-childbearing potential at Screening, Week 0/Day 1 and Follow-Up. The results must be negative for the patient to enroll and continue in the study.

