Appendix 2: Laboratory Specimen Collection (Part 1)

VISIT NAME	SCREENING	Week 0	Week 2	Week 4	Week 6	Week 8	Week 12/ET3	FOLLOW-UP
Study Day (Study day window ± 3 days)	-	Day 1	Day 14	Day 28	Day 42	Day 56	Day 84	-
Group Name(s)								
Chemistry Panel	X	X	X	X	X	X	X	X
Electrolyte Panel	X	X	X	X	X	X	X	X
Lipid Panel	X	X	-	X	X	-	X	-
Single point PK	-	X	X	X	X	X	X	-
Hematology & Differential Panel	X	X	X	X	X	X	X	X
Urine Panel	X	X	X	X	X	X	X	X
Single point Gluca/GLP-1	-	X					X	-
Single point c-peptide and retention	-	X	-	-	-	-	X	-
Lactate	-	X	X	X	X	X	X	-
Free Fatty Acids	-	X	-	X	X	-	X	-
HbA1C	X	X	X	X	X	X	X	-
Fructosamine	-	X	X	X	X	X	X	-
GLYCOMARK	-	X	X	X	X	X	X	-
BETA-HYDROXYBUTYRATE	-	X	X	X	X	X	X	X

C O N F I D E N T I A L

Investigational Product: TTP399
 Protocol Number: TTP399-203

Amendment5/FINAL
 Date: 08FEB2019

Laboratory Specimen Collection (Part 2)

VISIT NAME	SCREENING	Week 0	Week 2	Week 6	Week 12/ET3	FOLLOW-UP
		Study Day	Day 1	Day 14	Day 42	
Group Name(s)						
Chemistry Panel	X	X	X	X	X	X
Electrolyte Panel	X	X	X	X	X	X
Lipid Panel	X	X	X	X	X	X
Single point PK	-	X	-	X	X	-
Hematology & Differential Panel	X	X	X	X	X	X
Urine Panel	X	X	X	X	X	X
Lactate	-	X	X	X	X	X
Single point c-peptide	-	X	-	X	X	-
Single point Gluca	-	X	-	X	X	-
Single point retention	-	X	-	X	X	-
Free Fatty Acids	-	X	-	X	X	-
HbA1C	X	X	-	X	X	-
Fructosamine	-	X	-	X	X	-
GLYCOMARK	-	X	-	X	X	-
BETA-HYDROXYBUTYRATE	-	X	X	X	X	X

Chemistry panel: Total Bilirubin, Alkaline Phosphatase, ALT, AST, Urea Nitrogen, GGT, Creatinine, Uric Acid, Calcium, Total Protein, Albumin, Fasting plasma glucose and Direct bilirubin (Screening only)

Electrolyte panel: Sodium, Potassium, Bicarbonate, Chloride

Lipid panel: Cholesterol, Direct HDL Cholesterol, LDL Cholesterol Calculated, Triglycerides

Hematology & Differential Panel: Hemoglobin, Hematocrit, RBC, MCH, MCHC, RBC Morphology and MCV, WBC, Neutrophils, Lymphocytes, Monocytes, Eosinophils, Basophils and Platelets

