6.2.3 Clinical laboratory assessments

Clinical laboratory variables of analysis include raw means and mean changes from baseline for the clinical laboratory measures in this study

- Hematology: hemoglobin, hematocrit, RBC count, platelet count, WBC count, total neutrophils (abs), eosinophils (abs), monocytes (abs), basophils (abs), lymphocytes (abs)
- Clinical chemistry: BUN, creatinine, calcium (total), sodium, potassium, chloride, total carbon dioxide, (bicarbonate), AST (SGOT), ALT (SGPT), alkaline phosphatase (ALK), total bilirubin, direct (conjugated) bilirubin, uric acid, albumin, total protein
- Lipid panel: total cholesterol, HDL-C, LDL-C, triglycerides
- Specialty laboratory tests: HbA1c, C-peptide, lactate, ketones, free fatty acids, GGT, fructosamine, glucagon, 1, 5 anhydroglucitrol.

A treatment-emergent abnormal value (TEAV) is a laboratory analyte that is abnormal after administration of study medication that was not present prior to the administration of study medication.

Safety variables of analysis include:

- Proportions of patients with TEAVs
- Proportions of patients with a TEAV in any liver function test (LFT) including ALT, AST, total bilirubin, alkaline phosphatase.

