7.7.4 Clinical Laboratory Measurements

Because “exacerbations” of pre-existing abnormalities in laboratory analytes are examined using clinical judgment and are reported as TEAEs, additional analysis on TEAVs is limited to subjects with values that are normal prior to dosing and abnormal after dosing.

Adverse events of special interest also treatment-emergent abnormal values (TEAVs) in laboratory parameters related to liver function tests, specifically ALT, AST, bilirubin, and ALK.

Potentially clinically significant values in laboratory analytes will be examined in accordance with the table of values or changes of potential clinical significance in this SAP. Proportions of subjects in each treatment group who meet the criteria will be analyzed.

Laboratory data will be summarized by Baseline and change from Baseline to each scheduled assessment time with descriptive statistics.

Liver function tests have additional monitoring for this study.

To explore the potential for drug-induced liver injury consistent with *Guidance for Industry “Drug-induced liver injury: premarketing clinical evaluation”* (CDER, CBER, July 2009), subjects will be summarized and listed who meet the following criteria:

- (1) Elevations in either AST or ALT of at least 3-times the upper limit of normal, and

- (2) An accompanying abnormal bilirubin.

Additionally, a summary and listing will be examined for subjects with elevations in either AST or ALT of at least 3-times the upper limit of normal, regardless of bilirubin.

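### On-treatment direct bilirubin exists only for patients with raised total bilirubin, so its planned by-visit mean and mean change rise in both arms by selection alone

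*Protocol*

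**What the plan says.** Protocol 8.7.2, Table 2, footnote a, sets the sampling rule. "Direct bilirubin will be measured at Screening"; during treatment "both direct and indirect bilirubin will ONLY be measured when total bilirubin is greater than upper limit of the reference range". It then states the converse: "If total bilirubin is lower than the upper limit of the reference range, neither direct nor indirect bilirubin will be measured".

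Protocol Appendix 2 describes the schedule differently. Its definition of the chemistry panel ends "Fasting plasma glucose and Direct bilirubin (Screening only"), with no reflex test. Total bilirubin is in the same panel without that restriction, and the panel is drawn at Screening, Weeks 0, 2, 6 and 12 (or early termination) and follow-up in Part 2.

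SAP 6.2.3 defines the laboratory variables as "raw means and mean changes from baseline for the clinical laboratory measures in this study", and its clinical chemistry list includes "total bilirubin, direct (conjugated) bilirubin, uric acid, albumin, total protein". SAP 7.7.4 adds: "Laboratory data will be summarized by Baseline and change from Baseline to each scheduled assessment time with descriptive statistics". SAP 7.5 says that missing safety data are in general not imputed, and SAP 8.1 takes the safety baseline as the mean of all valid pre-dose values. No rule in the SAP exempts direct bilirubin or deals with the conditional sampling.

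**The concern.** Read together, these sections put two different groups of patients into one row of a table. The baseline mean comes from everyone. Each on-treatment mean comes only from patients whose total bilirubin was above the limit at that same visit. Because direct bilirubin is part of total bilirubin, choosing patients with a high total also chooses patients with a high direct value.

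The mean change is restricted to the same patients at both times, but that does not remove the problem. These patients were chosen on a high value at the later time and not at the earlier one, so regression to the mean makes the change positive.

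The drug is a liver-selective glucokinase activator, and SAP 7.7.4 treats abnormal liver tests as events of special interest. A table in which direct bilirubin appears to double on treatment in both arms would draw questions that the data cannot answer.

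**Working it through.** The documents state no mean, SD or rate for bilirubin, so there is no figure of the plan's own to reproduce. From the documents come the testing rule, the planned statistics and the Part 2 arm size of 45 (SAP 1.7). Everything else below is an assumption.

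**Direction.** Let T0 and T1 be standardized total bilirubin at baseline and at a visit, with correlation r, and let direct bilirubin have correlation rho with total at the same time. A value exists at the visit only if T1 > c. With no drug effect:

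- mean at the visit, relative to the all-patient mean = rho × E[T1 | T1 > c]
- mean change in those patients = rho × (1 − r) × E[T1 | T1 > c]

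The first is positive whenever direct and total are positively related. The second is also positive whenever r < 1. Neither sign depends on the numbers chosen.

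**Size in this model.** Assume 5% above the limit (c = 1.645), so E[T1 | T1 > c] = 2.063, with r from 0.5 to 0.8 and rho from 0.6 to 0.8. About 0.05 × 45 = 2.25 patients per arm contribute.

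| r | rho | visit mean (SD) | mean change (SD) |
|---|---|---|---|
| 0.8 | 0.6 | 0.6 × 2.063 = 1.24 | 0.6 × 0.2 × 2.063 = 0.25 |
| 0.8 | 0.8 | 0.8 × 2.063 = 1.65 | 0.8 × 0.2 × 2.063 = 0.33 |
| 0.5 | 0.6 | 1.24 | 0.6 × 0.5 × 2.063 = 0.62 |
| 0.5 | 0.8 | 1.65 | 0.8 × 0.5 × 2.063 = 0.83 |

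With direct bilirubin measured in everyone, both columns would be zero.

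**Size in a simulation on the mg/dL scale.** Assumptions: lognormal total bilirubin, log-SD 0.35 or 0.45; upper limit 1.2 mg/dL; 3%, 5% or 10% of patients above it; within-patient correlation 0.5 to 0.85; direct equal to 25% of total with lognormal noise (SD 0.25). Baseline was the Screening value, with and without a reflex Day 1 value averaged in. With no drug effect:

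- The baseline mean is 0.15 to 0.21 mg/dL and the visit mean 0.36 to 0.39, a ratio of 1.7 to 2.5.
- The mean change in tested patients is +0.02 to +0.13. With everyone measured it would be about 0 (−0.005 to 0.000).
- About 1 to 5 of 45 patients per arm contribute.
- In trials of 45 per arm, the placebo visit mean exceeded the baseline mean in over 99% of those with any value.

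**What the table does under a drug effect.** In the first model, let a general shift of 0.608 SD triple the share above the limit to 15% (0.15 × 45 = 6.75 patients). Then E[T1 | T1 > c] = 2.163, and the baseline total of those patients averages r × (2.163 − 0.608) = 1.555r. The mean change becomes rho × (2.163 − 1.555r):

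- r = 0.8, rho = 0.6: 0.6 × (2.163 − 1.244) = 0.55, against 0.25 with no effect.
- r = 0.5, rho = 0.8: 0.8 × (2.163 − 0.778) = 1.11, against 0.83.

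The visit mean moves little: 2.163 − 2.063 = 0.10, times rho, is 0.06 to 0.08 SD.

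**The case against.** The strongest reply is that little hangs on this table, and most of that reply stands.

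- Total bilirubin is measured at every laboratory visit. It carries the proportion of patients with a treatment-emergent abnormal liver test (SAP 6.2.3) and the clinical-concern threshold (SAP Section 14, which sets none for direct bilirubin). Bilirubin also enters the drug-induced liver injury summary (SAP 7.7.4).
- With no drug effect the selection works alike in both arms, so it produces a false trend within each arm and not a false difference between them.
- The summaries are descriptive and would rest on a handful of patients.

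A reader might go further and infer that the table would hardly register a tripling of raised bilirubin, or that it would hide a liver signal. The documents do not support either inference. The visit mean alone is insensitive to a general shift, but the mean change does move, as shown above. In the simulation the visit mean also rose by 19% to 37% when a susceptible subset drove the increase, and by 40% to 74% when all levels tripled. SAP Section 7 requires the number of observations to be displayed, and under footnote a that number is close to the count of patients above the limit, so it would go from about 2 to about 7. Total bilirubin would show the same signal.

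A reader might also infer that the proportion with an abnormal direct bilirubin is calculated among tested patients only. SAP Section 4 uses all dosed patients for safety analyses, which points the other way.

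Finally, if Appendix 2 is taken literally, the on-treatment cells are empty and not biased. That leaves two protocol statements in conflict, and under neither does the planned mean change describe the treated patients.

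**Conclusion.** The concern holds as a point about one descriptive table. Under footnote a, the by-visit mean and mean change of direct bilirubin are products of the testing rule and will tend to rise in both arms without any drug effect. Under Appendix 2 they cannot be computed at all.

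The direction requires only that direct and total bilirubin are positively related and that total bilirubin varies within patients. The size (a visit mean 1.7 to 2.5 times baseline, a mean change of +0.02 to +0.13 mg/dL) rests wholly on the assumed distribution and correlations.

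The importance is low: no efficacy result is affected, no false drug-placebo difference follows from the selection alone, and the liver signal is not lost. The change is still worth making, because it removes a biased summary at almost no cost.

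**What to change.** 1. In SAP 6.2.3 and 7.7.4, take direct bilirubin out of the by-visit mean and mean-change summaries.
2. In their place, list direct bilirubin and the direct fraction by arm for patients with raised total bilirubin, and show their number out of all treated patients in the arm.
3. Use total bilirubin, which everyone has, for trends over time.
4. Reconcile Protocol Table 2 footnote a with the chemistry panel definition in Appendix 2, and record which rule the laboratory followed.

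The cost is a few lines of SAP text, one listing shell and one protocol clarification. No new data are needed.
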